3.5.1. Adverse Events

An adverse event is considered treatment emergent (TEAE) if the event occurs during the on-treatment period.

3.5.2. Adverse Events of Special Interest (AESI)

AESIs include events such as CNS (mood, speech, cognition) events. These events will be defined based on a list of MedDRA Preferred Terms specified in the Safety Review Plan for lorlatinib. A final list will be provided to programming prior to database release.

3.5.3. Laboratory Data

Hematology, chemistry, lipids, coagulation and urinalysis result will be programmatically graded according to the NCI CTCAE version 4.03 for relevant parameters. A shift summary of baseline grade by maximum post-baseline grade will be presented. Parameters which cannot be graded will be summarized relative to the normal range (ie, normal range high or normal range low). Additional details are provided in [Section 6.5.3](#).

4. ANALYSIS SETS

Data for all subjects will be assessed to determine if subjects meet the criteria for inclusion in each analysis population prior to releasing the database and classifications will be documented per standard operating procedures.

4.1. Full Analysis Set

The full analysis (FA) set will include all patients who are enrolled, regardless of whether or not treatment was received.

4.2. Per Protocol (PP) Analysis Set

The per protocol analysis set will include all enrolled subjects with ALK positive NSCLC, received a prior ALK inhibitor as protocol required, and who received at least 1 dose of lorlatinib:

- In Cohort 1, received crizotinib as the only ALK inhibitor.
- In Cohort 2, received one ALK inhibitor other than crizotinib, with or without prior crizotinib treatment.

4.3. Safety Analysis(SA) Set

The safety analysis set includes all enrolled patients who receive at least one dose of lorlatinib.

4.4. Other Analysis Sets

4.4.1. Pharmacokinetics Analysis Set

The PK parameter analysis population is defined as all enrolled patients who receive at least one dose of study medication and have sufficient information to estimate at least 1 of the PK parameters of interest.

CCI

5. GENERAL METHODOLOGY AND CONVENTIONS

5.1. Hypotheses and Decision Rules

5.1.1. Hypotheses and Sample Size Section

Cohort 1:

The primary objective of the study is to evaluate the anti-tumor effect of lorlatinib as a single agent as measured by ORR per RECIST v1.1 in locally advanced or metastatic ALK-positive NSCLC patients whose disease has progressed after crizotinib treatment, ie, Cohort 1.

The study is designed to test the null hypothesis H_0 : $ORR \leq 30\%$ vs. H_A : $ORR > 30\%$. Assuming at least a 20% increase of ORR with lorlatinib treatment, 66 patients will be required to provide 90% power to reject the null hypothesis at a significance level of 0.025 (one-sided).

Cohort 2:

No formal statistical hypothesis testing is planned for Cohort 2. This cohort will explore the safety and efficacy of lorlatinib after one ALK inhibitor treatment other than crizotinib with 34 patients planned to be enrolled.

The sample size of 34 patients will provide the estimated ORR with a maximum width of the 95% CI of 35%, observed with 17 responses out of 34 patients. In order to collect more information of anti-tumor activity, if the patients received study treatment but without adequate baseline tumor assessment or without post baseline tumor assessments, additional patients may be allowed to be enrolled.

With approximately 66 and 34 patients in Cohort 1 and 2 respectively, this study will provide adequate sample size for safety evaluation with a minimal number of 100.

5.1.2. Decision Rules

Cohort 1 will test the null hypothesis H_0 : $ORR \leq 30\%$.

If at least 28 responses are observed among the 66 patients enrolled, then the null hypothesis will be rejected, and it will be concluded that the study has demonstrated that the true ORR exceeds 30%.

However, if the actual number of patients is not equal to 66 at the time of final analysis of ORR in Cohort 1, the testing will depend on the exact number of patients enrolled. If the p-value of the test < 0.025 , then the null hypothesis will be rejected.

5.2. General Methods

Unless otherwise specified, baseline data will be summarized by Cohort. Disposition, efficacy, exposure (including concomitant therapies), and safety data will also be summarized by Cohort and Total.

5.2.1. Data Handling after the Cut-off Date

Data after the cut-off date may not undergo the cleaning process and will not be displayed in any listings or used for summary statistics, statistical analyses or imputations.

5.2.2. Pooling of Data by Center

In order to provide overall estimates of treatment effects, data will be pooled across centers. The 'center' factor will not be considered in statistical models or for subset analyses due to the high number of participating centers in contrast to the anticipated small number of patients treated at each center.

5.2.3. Definition of Study Day

Start day of study treatment is the day of the first dose of study treatment.

The study day for assessments occurring on or after the first dose of study treatment (eg, adverse event onset, laboratory date, tumor measurement) will be calculated as:

$$\text{Study day} = \text{Date of the assessment/event} - \text{start date of study treatment} + 1.$$

The study day for assessments occurring prior to the first dose of study treatment (eg, baseline characteristics, medical history) will be negative and calculated as:

$$\text{Study day} = \text{Date of the assessment/event} - \text{start date of study treatment}.$$

The study day will be displayed in all relevant data listings.

5.2.4. Definition of Cycle and Cycle Day

Cycle start and end dates are derived per patient.

Lorlatinib is administered every 3 weeks in a cycle; therefore the nominal cycle length is 21 days.

For Cycle X, the actual cycle start date for each subject is the earliest start date of dosing (dose>0 at that visit) in Cycle X visit CRF exposure page.

- For all but the last cycle;
- Actual cycle stop date is calculated as the start date of the next cycle minus one day.
- Actual cycle duration is calculated from Day 1 of a cycle to the day prior to Day 1 of the next cycle, as follows:

$$\text{Actual Cycle Duration (weeks)} = (\text{cycle stop date} - \text{cycle start date} + 1) / 7$$

- For the last cycle, actual cycle duration is calculated as follows:

$$\text{Actual Cycle Duration (weeks)} = (\text{last date of study treatment} - \text{cycle start date} + 1) / 7$$

The cycle day will be calculated as:

$$\text{Cycle day} = \text{Date of the assessment/event} - \text{cycle start date} + 1.$$

5.2.5. Definition of Start of New Anti-cancer Drug Therapy

Start date of new anti-cancer drug therapy is used to determine the end of the on-treatment period (see [Section 3.5](#)).

The start date of new anti-cancer drug therapy is the earliest start date of anti-cancer drug therapy recorded in the 'Follow-up Cancer Therapy' eCRF pages that is after the first dose of study treatment. When start date of anti-cancer drug therapy is missing or partially missing, the imputation rules described in [Section 5.3.4](#) should be applied using only data from the 'Follow-up Cancer Therapy' eCRF pages.

5.2.6. Definition of Start of New Anti-cancer Therapy

Start date of new anti-cancer therapy (drug, radiation, surgery) is used for censoring in efficacy analyses (see [Section 6.2.6](#)).

The start date of new anti-cancer therapy is the earliest date after first dose amongst the following:

- Start date of anti-cancer drug therapy recorded in the 'Follow-up Cancer Therapy' eCRF pages.
- Start date of radiation therapy recorded in 'Concomitant Radiation Therapy', and 'Follow-up Radiation Therapy' eCRF pages with 'Treatment Intent' = 'Curative in intent'.
- Surgery date recorded in 'Concomitant Surgery', and 'Follow-up Surgery' eCRF pages when 'Surgery Outcome' = 'Resected' or 'Partially Resected'.

When start date of anti-cancer therapy is missing or partially missing, the imputation rules described in [Section 5.3.1](#) should be applied using 'Follow-up Cancer Therapy', 'Concomitant Radiation Therapy', 'Follow-up Radiation Therapy', 'Concomitant Surgery', and 'Follow-up Surgery' eCRF pages.

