5.9.3. Other Concomitant Medications and Therapies

Patients are prohibited from receiving the following therapies during the treatment phase of this trial:

- Anti-cancer systemic chemotherapy or biological therapy.
- Investigational agents other than lorlatinib.
- Radiation therapy (with the exception noted in the [Section 5.9.6](#)).
- Other experimental pharmaceutical products.
- Herbal remedies with anticancer properties or known to potentially interfere with major organ function or study drug metabolism (eg, hypericin).

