9.1. Sample Size Determination

The primary objective of the study is to evaluate the anti-tumor effect of lorlatinib as a single agent as measured by ORR per RECIST v1.1 in locally advanced or metastatic ALK-positive NSCLC patients whose disease has progressed after crizotinib treatment, ie, Cohort 1.

As of the original version date of protocol, given there's no ALK inhibitor other than crizotinib approved in China currently, chemotherapy is still considered as standard of care for patients progressed after crizotinib. Based on the current reported results, the ORR of chemotherapy in previous systemic treatment treated patients ranged from 6.9% - 20%.^{21,28,29} The ORR was 26.7% even for treatment naive patients.²² Therefore, ORR of 30% was chosen as the historical control for Cohort 1. The Fleming single stage design will be used to test the null hypothesis (H0) as of ORR \leq 30% with 1-sided 0.025 significance level. Assuming at least a 20% increase of ORR with lorlatinib treatment, 66 patients will be required to provide 90% power to reject the null hypothesis. Exact test will be performed at the time of the analysis. If at least 28 responses are observed among the 66 patients enrolled, then the null hypothesis will be rejected, and it will be concluded that the study has demonstrated that the true ORR exceeds 30%. However, at the time of the analysis, the testing will depend on the exact number of patients enrolled.

Cohort 2 will explore the safety and efficacy of lorlatinib in patients with locally advanced or metastasis ALK-positive NSCLC whose disease have progressed after one ALK inhibitor treatment other than crizotinib. As of the original version date of protocol, there was no approved ALK inhibitor other than crizotinib in China, therefore, the eligible patients were very limited and no established standard of care was available. Considering this limitation, Cohort 2 will be exploratory with about 34 patients planned to be enrolled. No specific statistical hypothesis will be tested. Descriptive analyses will be provided for the endpoints.

The sample size of 34 patients will provide the estimated ORR with a maximum width of the 95% CI of 35%, observed with 17 responses out of 34 patients. In order to collect more information of anti-tumor activity, if the patients received study treatment but without adequate baseline tumor assessment or without post baseline tumor assessments, additional patients may be allowed to be enrolled.

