3. ENDPOINTS AND BASELINE VARIABLES: DEFINITIONS AND CONVENTIONS

3.1. Primary Endpoint(s)

- Objective Response (OR) in patients whose disease have progressed after crizotinib (Cohort 1) by independent central radiology (ICR) assessment per RECIST v1.1. OR is defined as a complete response (CR) or partial response (PR) recorded from enrollment until disease progression or start of new anti-cancer therapy. Both CR and PR must be confirmed by repeat assessments performed no less than 4 weeks after the criteria for response are first met.

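### SAP 5.2.6 dates new anti-cancer drugs from follow-up pages only, so a prohibited anti-cancer drug or herbal remedy recorded solely as a concomitant medication would not close the response window for the primary ORR

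*SAP*

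**What the plan says.** SAP 3.1 defines objective response as a confirmed CR or PR "recorded from enrollment until disease progression or start of new anti-cancer therapy". The best overall response rules in SAP 6.1 repeat the limit: both determinations, at least 4 weeks apart, must come before progression and before new anti-cancer therapy.

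SAP 5.2.6 dates that therapy for efficacy purposes as the earliest qualifying date after first dose. For radiation and for surgery it reads both a concomitant and a follow-up page. For drugs it reads one source: "Start date of anti-cancer drug therapy recorded in the 'Follow-up Cancer Therapy' eCRF pages". Its list of pages for imputing incomplete dates has no concomitant medication page either. SAP 5.2.5, which ends the on-treatment period for safety, uses the same single drug source.

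Protocol 5.9.2 does not permit concurrent anti-tumor treatment. Protocol 5.9.3 names systemic chemotherapy, biological therapy, investigational agents and "Herbal remedies with anticancer properties or known to potentially interfere with major organ function or study drug metabolism" as prohibited during treatment. Protocol 5.9 has concomitant medications recorded in the CRF until 28 days after the last dose.

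The per-protocol set does not depend on prohibited therapy taken on study: "The per protocol analysis set will include all enrolled subjects with ALK positive NSCLC, received a prior ALK inhibitor as protocol required", plus at least one dose of lorlatinib.

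**The concern.** The endpoint definition excludes responses that follow another anti-cancer therapy, so that tumor shrinkage is credited to lorlatinib alone. The rule that dates such therapy has no concomitant source for drugs, although it has one for radiation and surgery. Elsewhere the documents treat the follow-up pages as post-treatment: SAP 6.4.5 classes them as subsequent therapy, and footnote 28 of the Schedule of Activities collects subsequent systemic treatment after lorlatinib stops. An anti-cancer drug or herbal remedy taken alongside lorlatinib could therefore be recorded only as a concomitant medication and be invisible to the response derivation.

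At stake is the Cohort 1 ORR and its test against 30%. A missed therapy can only leave in the numerator a patient whom SAP 3.1 would count as a non-responder, so the error in ORR runs upward.

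**Working it through.** **1. Which sources close the window (SAP 5.2.6)**

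| Modality | Concomitant page | Follow-up page |
|---|---|---|
| Radiation (curative intent) | yes | yes |
| Surgery (resected or partially resected) | yes | yes |
| Drug | no | yes |

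**2. Whether another planned analysis removes the patient**

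- Per-protocol ORR (SAP 4.2, 6.1.1): screens ALK status, prior ALK inhibitor and one dose. It does not.
- Full-analysis-set ORR (Protocol 9.3.1): includes everyone enrolled. It does not.
- Disagreement rate and derived mRECIST ORR (SAP 6.1.1, Appendix 1): address reader agreement and lesion selection. They do not.
- Protocol deviations (SAP 6.4.2.2) and concomitant medications (SAP 6.4.4): listed or tabulated. A case may be visible there, but the ORR is unchanged.

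**3. The plan's own design figures**

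Inputs: null ORR 30% ("Therefore, ORR of 30% was chosen as the historical control for Cohort 1", Protocol 9.1); alternative 30% + 20 points = 50% and N = 66 ("Assuming at least a 20% increase of ORR with lorlatinib treatment, 66 patients will be required to provide 90% power", SAP 5.1.1); test "with 1-sided 0.025 significance level" (Protocol 9.1); rule "If at least 28 responses are observed among the 66 patients enrolled, then the null hypothesis will be rejected" (SAP 5.1.2).

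Exact binomial, X ~ Bin(66, p):

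- P(X ≥ 28 | p = 0.30) = 0.0216, within 0.025.
- P(X ≥ 27 | p = 0.30) = 0.0386, above 0.025, so 28 is the correct boundary.
- P(X ≥ 28 | p = 0.50) = 0.912, consistent with the stated 90%.

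The design reproduces, and the fix leaves N, alpha, power and the boundary unchanged.

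**4. Effect of k affected responders**

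The documents give no frequency, so k = 0 to 3 is an assumed range. The shift in ORR is k/66. If k patients count as responders only through this gap and the others respond at 30%, the chance of rejecting the null is P(Bin(66 − k, 0.30) ≥ 28 − k).

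| k | ORR shift (points) | Chance of rejection when the others respond at 30% |
|---|---|---|
| 0 | 0 | 2.2% |
| 1 | 1.5 | 3.2% |
| 2 | 3.0 | 4.6% |
| 3 | 4.5 | 6.4% |

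**5. When the decision changes**

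Removing one responder at the boundary takes 28/66 (42.4%, exact 95% CI 30.3 to 55.2%, p = 0.0216) to 27/66 (40.9%, CI 29.0 to 53.7%, p = 0.0386). One patient matters only at exactly 28; in general, k patients matter only if the observed count lies between 28 and 27 + k. At a true ORR of 50%, the chance of exactly 28 responses is 0.912 − 0.866 = 4.6%, where 0.866 is P(X ≥ 29). At 33/66 (p = 0.0005) a few such patients would not change the decision.

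**6. Direction for PFS**

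SAP 6.2.6 censors PFS at the last adequate assessment before new therapy, so a missed therapy can keep a later progression as an event. Take five patients with events at months 2, 4, 6, 8 and 10: the Kaplan-Meier median is 6. Now censor the month-6 patient at month 3. Survival is 4/5 = 0.800 after month 2, 0.800 × 2/3 = 0.533 after month 4 and 0.533 × 1/2 = 0.267 after month 8, so the median becomes 8. Detecting the therapy can thus lengthen PFS. The same holds for DoR if it is censored in the same way, a rule that SAP 6.2.3 does not state.

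**The case against.** The strongest reply is that the protocol already routes these cases to the follow-up pages. Concurrent anti-tumor drugs are not permitted at all, whereas surgery and palliative radiotherapy can occur on treatment (Protocol 5.9.5, 5.9.6), which would explain why only those two have a concomitant source. A decision to give alternative anti-cancer therapy triggers the end-of-treatment visit (Protocol 7), and a significant protocol violation is a listed reason to stop treatment (Protocol 6.4). This makes follow-up recording likelier for an ordinary systemic anti-cancer drug. None of it is a data rule, however, and a herbal remedy or short course taken while lorlatinib continues is not covered. The SAP also does not say whether a herbal remedy counts as anti-cancer drug therapy.

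A reader might infer that a drug taken during lorlatinib can never close the window. The documents do not support that: SAP 5.2.6 is anchored to first dose, not last dose, so an on-treatment start date entered on the follow-up page counts. The CRF and its completion rules are not among the documents, so the page actually used is an inference.

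SAP 5.2.6 gives its use as censoring and cross-refers only to 6.2.6, the PFS section. Its application to ORR rests on the shared term in 3.1 and 6.1. That stands, and it is a reason to add the cross-reference.

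A reader might also infer that the gap can only lengthen PFS and DoR. Step 6 of the working shows that it need not.

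**Conclusion.** The gap is real but conditional. It operates only if a prohibited anti-cancer drug or anti-cancer herbal remedy is taken while lorlatinib continues, is recorded only as a concomitant medication, and is followed by the first or the confirming CR or PR determination. Such a patient would count as a responder against the plan's own definition, and no planned sensitivity ORR would remove the case.

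The bias in ORR is upward, 1.5 points per affected patient out of 66. How many such patients there would be cannot be derived from the documents, and nothing in them shows that such cases occurred. The test result is at risk only close to the boundary of 28, which itself moves if Cohort 1 does not have exactly 66 patients. For PFS and DoR the direction is not fixed. This is an inexpensive alignment of the derivation with the endpoint definition; it is not evidence that the primary result would be wrong.

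**What to change.** - In SAP 5.2.6, add to the drug source, and to the list of pages used for date imputation, any systemic anti-cancer drug or anti-cancer herbal remedy in the Protocol 5.9.2 and 5.9.3 categories that is started after first dose and recorded on the concomitant medication pages.
- Identify these by medical review of the coded terms before database release and without reference to response.
- Cite 5.2.6 from the best overall response rules in 6.1, so that one date governs ORR as well as PFS, and state that it applies to DoR.
- In 5.2.5, state whether the same source also ends the on-treatment period. That section points to 5.3.4 (missing ECG data) for date imputation, while the rules are in 5.3.1; this can be corrected in the same edit.

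The cost is a few sentences in the SAP and a short medical review of data already collected and, under SAP 6.4.4, already due for WHO Drug coding. The downsides are that ORR may fall slightly if cases exist and that a few more PFS or DoR times may be censored. If there are no cases, no result changes.

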5.9.6. Concomitant Radiotherapy

Radiation therapy during the treatment phase is not allowed, with the exception described as below.

Palliative radiotherapy to specific sites of disease is permitted if considered medically necessary by the treating physician. All attempts should be made to rule out disease progression in the event of increased localized pain. If palliative radiotherapy is needed to control bone pain, the sites of bone disease should be present at baseline, otherwise, bone pain requiring radiotherapy will be considered as a sign of disease progression.

In view of the current lack of data about the interaction of lorlatinib with radiotherapy, lorlatinib treatment should be interrupted during palliative radiotherapy, stopping 1 day before and resuming treatment after recovery from acute radiation toxicities to baseline.

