3.2. Secondary Endpoint(s)

- OR in patients whose disease have progress after ALK inhibitor treatment other than crizotinib (Cohort 2) as assessed by RECIST v1.1 per ICR assessment.

- Progression-free survival (PFS) based on ICR assessment and investigator assessment by RECIST v.1.1 is defined as the time from first dose to first documentation of objective disease progression or to death due to any cause, whichever comes first in both Cohort 1 and Cohort 2.

- Overall Survival (OS) is defined as the time from first dose to the date of death due to any cause.

- Intracranial objective response(IC-OR)

IC-OR is defined the same as OR, but limited to Intra Cranial lesions only on patients with CNS metastases (ie, Best Overall Intracranial Response as confirmed CR or confirmed PR considering only the lesions having disease site as Brain).

- Duration of response (DoR)

DoR is defined as the time from the first documentation of CR or PR to the first documentation of disease progression or death due to any cause, whichever occurs first.

- Duration of intracranial response(IC-DoR)

IC-DoR is defined the same as DoR, but limited to Intra Cranial lesions only on patients with CNS metastases (ie, Best Overall Intracranial Response as confirmed CR or confirmed PR considering only the lesions having disease site as Brain).

- Time to tumor response (TTR)

TTR is defined as the time from first dose to first documentation of objective tumor response (CR or PR).

- PK: parameters on day 1 of cycle 1 and at steady state: C_{max} , T_{max} , AUC_t , AUC_{tau} at steady state, AUC_{inf} , CL/F , Vz/F , $t_{1/2}$ and R_{ac} as data permit.

CCI

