6. ANALYSES AND SUMMARIES

All efficacy analyses will be performed by Cohort on the SA set.

Radiographic images and clinical information collected on study will be reviewed by an ICR. ICR assessment will be used for the primary analysis of OR and for all secondary endpoints based on radiological assessments of tumor burden (ie, IC-OR, DoR, IC-DoR, TTR and PFS). These endpoints will also be derived using the local radiologist's/investigator's assessment.

6.1. Primary Endpoint(s): Objective Response in Cohort 1

The primary efficacy analysis will evaluate the anti-tumor effect of lorlatinib as a single agent as measured by OR per RECIST v1.1 in locally advanced or metastatic ALK-positive NSCLC patients whose disease has progressed after crizotinib treatment.

OR is defined as a complete response (CR) or partial response (PR) recorded from enrollment until disease progression or start of new anti-cancer therapy. Both CR and PR must be confirmed by repeat assessments performed no less than 4 weeks after the criteria for response are first met.

Objective Response Rate (ORR) is defined as the percentage of patients with a best overall confirmed response of CR or PR according to RECIST v1.1 relative to the total patients in the analysis population. Patients without documented CR or PR will be considered as non-responders. Additionally, patients with inadequate data for tumor assessment (eg, no baseline assessment or no follow-up assessments) will be considered as non-responders. The primary evaluation of ORR will be based on ICR's review relative to the SA set.

The exact test will be performed to test the null hypothesis $H_0: ORR \leq 30\%$. One-sided p-value will be provided together with the estimate of ORR and the corresponding exact 95% CI.

Best overall response (BOR) will be assessed based on reported overall responses at different evaluation timepoints by the independent radiologist and by the investigator from the date of first dose until documented disease progression or start of new anti-cancer therapy, according to the following rules:

- CR = at least two determinations of CR at least 4 weeks apart and documented before progression and start of new anti-cancer therapy.
- PR = at least two determinations of PR or better (and not qualifying for a CR) at least 4 weeks apart and before progression and start of new anti-cancer.

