6.2.2. Intracranial Objective Response (IC-OR) in Both Cohorts

The IC-OR, will be summarized similar to OR as described above in the subset of the SA population with at least 1 intracranial lesion.

Intracranial ORR is defined as the percent of patients with intracranial response (ie, Best Overall Intracranial Response as confirmed CR or confirmed PR considering only the Lesions having Disease Site=Brain) relative to patients with Brain lesions at study entry, and will be provided along with the corresponding 95% confidence interval. This includes patients for whom the brain lesions have been chosen as RECIST target lesions or not. Surgery or radiotherapy of extracranial lesions will not affect the determination of IC-OR.

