6.2.4. Duration of Intracranial Response (IC-DoR) in Both Cohorts

The IC-DoR, will be summarized similar to DoR as described above in the subset of the SA population with at least 1 intracranial lesion. Surgery or radiotherapy of extracranial lesions will not affect the determination of IC-DoR.

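### The SAP has no rule for brain radiotherapy in the intracranial response analysis, so a response first seen after palliative brain irradiation can be counted as IC-OR

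*SAP*

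**What the plan says.** SAP 3.1 counts a CR or PR "recorded from enrollment until disease progression or start of new anti-cancer therapy", and the best-response rules in SAP 6.1 require a confirmed CR to be "documented before progression and start of new anti-cancer therapy", with matching wording for PR. SAP 3.2 carries this over: "IC-OR is defined the same as OR, but limited to Intra Cranial lesions only on patients with CNS metastases".

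SAP 5.2.6 defines the start of new anti-cancer therapy. It says that the date "is used for censoring in efficacy analyses" and points to 6.2.6 (PFS). Three items set the date: follow-up anti-cancer drugs; surgery with complete or partial resection; and radiotherapy, but only from "eCRF pages with 'Treatment Intent' = 'Curative in intent".

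Protocol 5.9.6 forbids radiotherapy during treatment with one exception: "Palliative radiotherapy to specific sites of disease is permitted if considered medically necessary by the treating physician". No site is excluded. The need for radiotherapy is treated as a sign of progression only for bone pain at sites not present at baseline.

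On local therapy, SAP 6.2.2 has one sentence: "Surgery or radiotherapy of extracranial lesions will not affect the determination of IC-OR". SAP 6.2.4 has its counterpart: "Surgery or radiotherapy of extracranial lesions will not affect the determination of IC-DoR". Neither section says what happens when a brain lesion itself is irradiated.

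**The concern.** The intracranial response rate is a secondary endpoint, estimated with a confidence interval and no control arm, and it will be read as the drug's activity in the brain. A brain lesion that shrinks after irradiation says little about the drug. If such shrinkage can be scored as a response, nothing in a single-arm design offsets it, and the error goes one way only. The SAP authors evidently saw that local therapy bears on these endpoints, because they wrote an exemption for extracranial treatment. They did not write the rule for the intracranial case, where the attribution problem lies.

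**Working it through.** **Step 1: trace the definitions for one patient.** Take a patient with a baseline brain lesion, no intracranial response so far and no progression, who receives palliative brain radiotherapy on study.

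- Is this new anti-cancer therapy? Under SAP 5.2.6, no: the intent is not curative. SAP 5.2.5 defines a separate drug-only date for the safety period and would not catch it either.
- Is it progression? Protocol 5.9.6 has no statement for the brain like the one for bone pain at new sites.
- Does the lesion become non-evaluable? Neither Protocol Appendix 3 nor SAP 5.2.12 (adequate post-baseline assessment) says so.
- Does eligibility guard against it? Inclusion criterion 4 concerns previous irradiation of the required extracranial target lesion. It covers neither brain lesions nor irradiation during the study.
- Does SAP 6.2.2 or 6.2.4 cover it? No. Their exemption is for extracranial lesions.

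The window therefore stays open, and two later determinations of PR or better at least 4 weeks apart qualify as IC-OR. Brain radiotherapy with curative intent and brain resection are already caught by 5.2.6, so the gap is palliative-intent brain radiotherapy.

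**Step 2: reproduce the documents' own intracranial figure.** Protocol 1.2.3.4 gives 48 CR and 42 PR among 165 Phase 2 patients with CNS metastases in Study B7461001. (48 + 42)/165 = 90/165 = 54.5%, with exact 95% CI 46.6 to 62.3, as printed. The documents give no target, power or sample size for IC-OR in the present trial.

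**Step 3: assumed denominators.** The share with brain lesions is taken from the same study: 165/274 = 60.2%. That Phase 2 population mixed ALK-positive and ROS1-positive patients, so this is an assumption, and it is varied below. At 60%, 0.60 × 66 ≈ 40 in Cohort 1 and 0.60 × 34 ≈ 20 in Cohort 2. A rate near 54.5% gives about 22/40 and 11/20.

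**Step 4: effect of reclassifying one patient** (shift = 100/n points; Clopper-Pearson 95% CI).

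| Cohort | Counted as written | One patient removed | Shift |
|---|---|---|---|
| 1 | 22/40 = 55.0% (38.5 to 70.7) | 21/40 = 52.5% (36.1 to 68.5) | 2.5 |
| 2 | 11/20 = 55.0% (31.5 to 76.9) | 10/20 = 50.0% (27.2 to 72.8) | 5.0 |

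**Step 5: range.** If 40% to 80% have brain lesions, n is 26 to 53 in Cohort 1 and 14 to 27 in Cohort 2. The shift per patient is then 100/26 = 3.8 down to 100/53 = 1.9 points, and 100/14 = 7.1 down to 100/27 = 3.7 points. The documents give no rate of on-study brain radiotherapy, so the total bias cannot be estimated.

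**The case against.** Five points can be made against this.

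1. *The main IC-OR analysis is the central read.* SAP 5.2.9 says that the independent radiologist also uses additional clinical information, and Protocol 7.1 defers imaging detail to an Imaging Charter that is not among the documents. Some SAP text near 6.2.6 and 6.3 is also redacted. A rule may exist there. This stands as a limit on the claim for the central read. It does not help the investigator-based IC-OR, also a secondary endpoint, where SAP 5.2.9 describes response derived by program from lesion data on the CRF.

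2. *SAP 5.2.6 may not govern the response window.* It cites only 6.2.6, and 6.1 does not cite it. Applying it to 6.1 is an inference. If it does not apply, the term in the OR definition has no visible meaning for radiotherapy, and that ambiguity also needs settling.

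3. *Exempting extracranial treatment implies that intracranial treatment matters.* It does suggest that. But it does not say whether such treatment closes the window, makes the lesion non-evaluable or censors the patient, so a programmer has nothing to apply.

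4. *The route is narrow.* At entry, CNS metastases must be asymptomatic, or treated with recovery. On study, the patient must have neither responded nor progressed in the brain on 6-weekly imaging, be irradiated with palliative intent anyway, and then show a confirmed response. This stands.

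5. *The effect is small against the uncertainty.* One patient moves Cohort 1 by 2.5 points inside an interval 70.7 − 38.5 = 32.2 points wide, and no decision rule depends on IC-OR. This also stands, and it makes the matter low priority.

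**Conclusion.** The gap is real on the visible text, but of low severity. A post-irradiation intracranial response can count in the programmed investigator-based analysis. It can also count in the central analysis unless the charter or the clinical information given to the readers prevents it. Both statements read 5.2.6 into 6.1. Each such patient would raise the intracranial response rate by about 2.5 points in Cohort 1 and 5.0 in Cohort 2, under the assumed 60% share with brain lesions.

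A reader might infer three stronger things that the documents do not support.

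- *That the centrally reviewed intracranial rate is inflated.* That depends on a charter not available here and on an unknown number of patients.
- *That the primary test in Cohort 1 is compromised.* Overall OR needs a confirmed fall of at least 30% in the whole target-lesion sum without progression anywhere, so irradiating one brain site seldom suffices. There is no basis for a type I error claim.
- *That the SAP deliberately credits irradiated lesions to the drug.* The text is silent on the case.

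**What to change.** 1. In SAP 6.2.2, state that for IC-OR any brain-directed radiotherapy, whatever its intent, closes the response window. A CR or PR first met after it does not count; one confirmed before it does. Where the response was first met before radiotherapy and only the confirming scan follows, do not count it in the main analysis, and show the result with it counted as a sensitivity analysis.
2. In SAP 6.2.4, keep the main IC-DoR rule and add one sensitivity analysis that censors at brain radiotherapy. Such censoring may be informative, so it should not be the main rule.
3. In SAP 6.1, state that 5.2.6 defines the term used there, with the IC-OR rule above as the exception. Align the text with the Imaging Charter, and report the number of patients affected.

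The cost is SAP wording and modest programming. The rule needs the irradiated site to be recorded: SAP 5.2.6 shows an intent field, but no site field is visible, so this should be checked first. The statistical price is a slightly lower intracranial response rate and fewer patients in IC-DoR; the confirming-scan rule is conservative, which is why the alternative is shown. The primary test, PFS, overall DoR and the protocol's clinical radiotherapy rules stay as they are.
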